#### 4.1.3.3 Selection of phase II dosing schedule

The decision on dose escalation/deescalation, MTD and RP2D will be determined in discussion with steering committee comprised of at least BI Trial Clinical Monitor, BI project physician (TMM) and Coordinating Investigator and taking into account patient safety. This decision will be documented.

#### 4.1.4 Drug assignment and administration of doses for each patient

The treatment medication assignment for BI 836845 and everolimus, if supplied by BI, will be managed through IRT system. However, if everolimus is used on label in the phase II part, it will be prescribed by the investigator and supplied by a pharmacy in some countries; under this circumstance, everolimus will not be managed through IRT system. Exemestane will not be supplied by the sponsor throughout the study; therefore, it will not be managed through IRT system.

Proprietary confidential information.

© 2016 Boehringer Ingelheim International GmbH or one or more of its affiliated companies. All rights reserved.

This document may not - in full or in part - be passed on, reproduced, published or otherwise used without prior written permission.

In addition, patient's screening, run-in, randomization, all drug dispensation visits and EOTV will be collected in the IRT system.

#### 4.1.4.1 Initial study drug assignment and administration

General information that applies in this study regardless of IRT is described in below sections of individual study drug. The medication kit as well as the treatment will be assigned with the support from IRT. The detailed information regarding handling of medication number will be described in ISF.

Before entering patients at the next dose level of the phase I part, it will be ensured that all patients at the current ongoing dose level have completed at least one course of treatment.

##### 4.1.4.1.1 BI 836845

Patients will start treatment with their assigned dose tier (see [Section 4.1.3](#)) or RP2D of BI 836845 from course 1 day 1. BI 836845 will be administered at the investigator site intravenously over one hour with a constant infusion rate on the treatment day as specified in the [Flow Chart](#). If scheduled infusion of BI 836845 is not performed within the time window, this treatment will be skipped and will not be made up. Subsequent visits should follow the original visit date schedule. Mannitol is used in the formulation of BI 836845, so an infusion duration of less than one hour must be avoided. The infusion time may be extended to over one hour and up to a maximum of three hours in cases of CTCAE grade  $\geq 2$  infusion reactions (see [Section 4.4.2](#) for grading and management of infusion reactions). Further information on infusion equipment and procedure is described in the ISF. In case of a delay or an interruption of infusion, the reason and the exact time of deviation must be recorded in the eCRF. The accuracy of this information is crucial for the proper evaluation and appraisal of the pharmacokinetics and other data.

**At days of PK sampling during the Phase I and II part, everolimus and exemestane should be administrated within 5 minutes after start of BI 836845 infusion.**

Detailed information of dispensation, preparation, and handling of BI 836845 will be described in ISF.

##### 4.1.4.1.2 Everolimus

Everolimus should be taken orally once daily after a meal at the same time every day. The blisters for everolimus tablets should be opened only at the time of administration as drug is both hygroscopic and light-sensitive. All blisters will conform to local regulatory requirements. The tablets should not be crushed or chewed. Everolimus should be swallowed whole with a large glass of water.

**At days of PK sampling, patients should NOT take study medication at home prior to their visits to the study site.**

Proprietary confidential information.

© 2016 Boehringer Ingelheim International GmbH or one or more of its affiliated companies. All rights reserved.

This document may not - in full or in part - be passed on, reproduced, published or otherwise used without prior written permission.

Missed doses of everolimus can be made up if taken within 6 hours of the regularly scheduled time. Otherwise, the dose should be skipped and patients should take the next scheduled dose at the usual time. Patients must not take 2 doses to make up for the missed dose. **Missed doses of everolimus should be recorded in the eCRF throughout the study.**

Everolimus will be prescribed by the investigator. If everolimus is supplied by the sponsor, it will be dispensed at visits described in [Flow Chart](#) either by the investigator, site staff or affiliated pharmacy through IRT. Otherwise, the prescription of everolimus should be filled by pharmacy. During the study, patients may be administered a combination of different dose strengths of everolimus to reach the expected dose level as outlined per protocol. For example, 10 mg everolimus can be given with two tablets of 5 mg or one tablet of 5 mg plus two tablets of 2.5 mg.

#### 4.1.4.1.3 Exemestane

The recommended treatment dose for exemestane is one 25 mg tablet once daily after a meal. Complete guidelines for management and administration of exemestane can be found in EU Summary of Product Characteristics or the prescribing information of respective country.

At days of PK sampling, **patients should NOT take study medication at home prior to their visits to the study center.**

Missed doses of exemestane can be made up if taken within 6 hours of the regularly scheduled time. Otherwise, the dose should be skipped and patients should take the next scheduled dose at the usual time. Patients must not take 2 doses to make up for the missed dose. **Missed doses of exemestane should be recorded in the eCRF throughout the study.**

There will be no investigational supply of exemestane. Exemestane will be prescribed by the investigator at visits described in [Flow Chart](#) and filled by pharmacy.

#### 4.1.4.1.4 Special instructions for the Run-in period and up to Course 1 Day 8 of the Phase I part

During the study period critical for DDI analysis (Run-in period and up to Course 1 Day 8 of the Phase I part), the timing of drug administration and food intake are specified in the following:

Patients should be advised to take everolimus and exemestane at approximately the same clock time in the morning after breakfast when taking study drugs at home.

At days of PK sampling critical for DDI analysis (**on Day -1 of Run-in and C1D1, C1D2 of the Phase I part, patients need to come fasted to the study site and should not take study medication at home prior to their visits.** Breakfast should be taken at approximately the same clock time on these days. The content and amount of the breakfast must be as close as possible on Day -1 of Run-in and C1D1, i.e. containing the same ingredients in a very similar amounts.

Proprietary confidential information.

© 2016 Boehringer Ingelheim International GmbH or one or more of its affiliated companies. All rights reserved.

This document may not - in full or in part - be passed on, reproduced, published or otherwise used without prior written permission.

The breakfast and drug administration should be timed according to the following schedule:

1. Patients start breakfast 30 min prior to start of infusion AND/OR 35 min prior to administration of everolimus and exemestane. Patients should complete their breakfast within 25 min
2. The pre-treatment sample should be taken 5 min prior to BI 836845 infusion AND/OR 10 min prior to administration of everolimus and exemestane.
3. 5 min after start of infusion AND/OR 35 min after start of breakfast, everolimus and exemestane are administered.

Information on drug and food intake during the Run-in and up to C1D8 should be recorded on the diary card and the eCRF.

**Sites should be encouraged to schedule PK visits in the early morning to accommodate consistent dosing schedules.**

#### 4.1.4.2 Additional course of treatment in Phase I part

The dose of BI 836845, everolimus and exemestane assigned upon entry to this trial will be used on all the scheduled administrations described in the Flow Chart unless the patient experienced DLT or treatment related adverse events which require dose modification.

Patients demonstrating a clinical benefit (i.e., with either an objective tumor response or the absence of disease progression) with the trial drug, and who have recovered from any clinically relevant drug-related AE, are eligible for further treatment courses as per the Flow Chart, until any of the conditions in Section 3.3.4.1 is met.

#### 4.1.4.3 Temporary treatment interruption and dose reduction

DLT or those AEs requiring dose adjustment as indicated on the label, should be managed by treatment interruptions and subsequent dose reductions of the presumed causal study drug(s) according to the schedule described in Table 4.1.4.3: 1. Please also refer to Section 4.4 for additional recommendations. In Phase I, both BI 836845 and everolimus must be paused when DLT occurs during the first treatment course.

To prevent the development of more severe adverse events, treatment related stomatitis, non-infectious pneumonitis and metabolic events should be closely monitored and managed early as described in Section 4.4.

The treatment should be paused until patient has recovered from the drug-related toxicity to grade  $\leq 1$  or baseline. Baseline is defined as the CTCAE grade at the start of treatment. For patients who develop DLT, treatment may be resumed at reduced dose according to dose reduction scheme of the patient's starting dosage. If a patient has not recovered to Grade  $\leq 1$  or baseline within 28 days, study treatment must be permanently discontinued. In the event

Proprietary confidential information.

© 2016 Boehringer Ingelheim International GmbH or one or more of its affiliated companies. All rights reserved.

This document may not - in full or in part - be passed on, reproduced, published or otherwise used without prior written permission.

that the patient is deriving obvious clinical benefit according to the investigator's judgement, further treatment with study drug(s) will be decided in agreement between the sponsor and the investigator.

Dose reductions will apply to individual patients only. Doses of BI 836845 and/or everolimus can be reduced independent of each other. Once the treatment dose is reduced for a particular patient, it should not be increased back to the previous dose.

Table 4.1.4.3: 1 Dose reduction scheme

Dose level	BI 836845	BI 836845	Everolimus dose (1)	Everolimus dose(2)	Everolimus dose (3)
0 = starting dose	1000 mg	750 mg	10 mg daily	7.5 mg daily	5 mg daily
-1 dose level	750 mg	500 mg	5 mg daily	5 mg daily	2.5 mg daily
-2 dose level	500 mg	Off-drug	2.5 mg daily	2.5 mg daily	2.5 mg every other day

Stomatitis, non-infectious pneumonitis, and metabolic events including hyperglycemia and dyslipidemia are common side-effects of everolimus listed on drug label. Please refer to the current everolimus prescribing information for dose adjustment recommendations (except for the Course 1 of the Phase I part where DLT occurs, in which both drugs need to be interrupted until AE recovery, refer to [section 5.2.6](#)). When these AEs occur and are considered related to study treatment, first dose modification is recommended to be made to everolimus preferentially.

No dose reduction is allowed below 500 mg for BI 836845 or 2.5 mg every other day for everolimus.

Alternative dose modification scheme can only be considered after discussion and agreement between the investigator and the BI clinical monitor.

Management of everolimus related adverse reaction and dose adjustment should be based on the European SPC or current prescribing information for everolimus of respective country or institutional standard, except for the Course 1 of the phase I part, for which, protocol should be followed in case of DLT.

Patients who need to reduce the dose of the same drug for more than two times should be discontinued from that drug treatment. Exception to this in patients who derive obvious clinical benefit according to the investigator's judgement could be considered upon discussion with BI's Clinical Monitor.

During temporary treatment interruption of BI 836845, the scheduled drug infusion will be missed and will not be administered retrospectively.

Proprietary confidential information.

© 2016 Boehringer Ingelheim International GmbH or one or more of its affiliated companies. All rights reserved.

This document may not - in full or in part - be passed on, reproduced, published or otherwise used without prior written permission.

In the event of any unrelated AEs or related non-DLT AEs, the study drug(s) may be interrupted for up to 28 days, but no dose reduction should occur unless indicated in the current drug label/SPC of everolimus or exemestane. Otherwise, the decision to continue with the study treatment will be made by the BI Clinical Monitor in agreement with the investigator.

#### **4.1.5 Blinding and procedures for unblinding**

##### **4.1.5.1 Blinding**

This is an open-label study. Blinding is not applicable. However, to reduce bias, the BI trial team will be blinded for the aggregated phase II part data at the treatment level until the trial database lock for the primary readout.

The prespecified looks by the DMC (see [section 7.3.4](#)) will not lead to an unblinding of the trial team in order to prevent potential introduction of operational bias. A logistics plan prepared and approved in accordance with BI's specific procedures will detail procedures used to ensure that all members of the trial team remain blinded. All subsequent actions requested by the DMC will be performed by an independent team as defined in the DMC charter. The logistics plan will also contain a detailed list of functions that need to be unblinded to perform this analysis.

##### **4.1.5.2 Procedures for emergency unblinding**

This is an open-label study. Procedures for emergency unblinding are not applicable.

#### **4.1.6 Packaging, labelling, and re-supply**

For details of packaging and the description of the label, refer to the ISF.

For details of drug supply, refer to [Section 4.1.1](#).

Boxes and vials of BI 836845 and boxes of everolimus (if supplied by BI) will be labelled according to local regulations and will include the following as a minimum:

- The study number (1280.4)
- Product name
- Contents of the bottle/carton box
- Strength
- Batch number
- Use-by date
- Storage information
- Instructions for use
- Sponsor name and address
- A statement indicating that the medication is for clinical trial use only
- A caution statement

Proprietary confidential information.

© 2016 Boehringer Ingelheim International GmbH or one or more of its affiliated companies. All rights reserved.

This document may not - in full or in part - be passed on, reproduced, published or otherwise used without prior written permission.

Examples of the labels will be filed in the ISF.

The BI 836845 and Everolimus (if provided by BI) drug supply will be managed through Interactive Response Technologies (IRT) by the study sites and BI personnel. Refer to the ISF for details of packaging and the description of the label as well as the process for resupply of study drug.

#### **4.1.7 Storage conditions**

BI 836845 and everolimus (for those provided by the sponsor) must be kept in a secure, limited access storage area under the storage conditions defined on the drug label. Temperature logs must be maintained to assure that drug supplies are stored at the correct temperature. If the storage conditions are found to be outside the specified range, immediately contact the local clinical monitor as provided in the list of contacts.

Investigational drug supply of BI 836845 and everolimus must be stored in the original packaging.

#### **4.1.8 Drug accountability**

The investigator or the pharmacist or investigational drug storage manager will receive the investigational drugs delivered by the sponsor when the following requirements are fulfilled:

- Approval of the study protocol by the IRB / ethics committee,
- Availability of a signed and dated clinical trial contract between the sponsor and the Head of Trial Centre,
- Approval/notification of the regulatory authority, e.g. competent authority,
- Availability of the curriculum vitae of the principal investigator,
- Availability of a signed and dated clinical trial protocol or immediately imminent signing of the clinical trial protocol,
- If applicable, availability of the proof of a medical licence for the principal investigator.

The investigator or pharmacist must maintain records of the product's delivery to the trial site, the inventory at the site, the use by each patient, and the return to the sponsor or alternative disposition of unused products.

These records will include dates, quantities, batch/serial numbers, expiry ('use by') dates, and the medication kit numbers assigned to the investigational products and trial patients. The investigator / pharmacist / investigational drug storage manager will maintain records that document adequately that the patients were provided the doses specified by the CTP and reconcile all investigational product(s) received from the sponsor. The investigator / pharmacist / investigational drug storage manager must verify that all unused or partially used drug supplies have been returned by the clinical trial patient.

**Proprietary confidential information.**

**© 2016 Boehringer Ingelheim International GmbH or one or more of its affiliated companies. All rights reserved.**

This document may not - in full or in part - be passed on, reproduced, published or otherwise used without prior written permission.

Any opened vials of BI 836845 should be discarded after use following local regulations and local hospital practices.

## **4.2 CONCOMITANT THERAPY, RESTRICTIONS, AND RESCUE TREATMENT**

### **4.2.1 Rescue medication, emergency procedures, and additional treatment(s)**

#### **4.2.1.1 Rescue medication**

Rescue medications to reverse the effects of BI 836845, everolimus, and exemestane are not available. Side effects of these treatments should be treated symptomatically with treatment interruption and dose reduction when needed. There is no specific antidote to overdosage of everolimus or exemestane.

#### **4.2.1.2 Emergency procedures**

There are no special emergency procedures to be followed.

Precaution should be taken to avoid extravasation of BI 836845. Patients should be asked to report any pain or burning at the site of injection immediately. If extravasation is suspected the infusion should be stopped immediately. Treatment should be reinitiated according to local practice.

#### **4.2.1.3 Concomitant treatments**

Symptomatic treatments of tumor-associated symptoms are allowed. Concomitant medications or therapy to provide adequate supportive care may be given as clinically necessary.

After study enrollment, palliative radiotherapy may be given for analgesic purposes, lytic lesions at risk of fracture or for other reasons (e.g. bronchial obstruction, skin lesions), provided that the total dose delivered is in a palliative range to non-target lesion according to institutional standards. Information on palliative radiotherapy will be captured in e-CRF. It is at the investigator's discretion to withhold the study treatment during palliative radiotherapy. The investigators should assess the signs/symptoms carefully to exclude the progressive disease prior to the administration of the palliative radiotherapy.

The acute use of bisphosphonates for symptomatic treatment of bone metastases is permitted during the study, but chronic use for the prevention of bone metastases is prohibited (see [Section 4.2.2.1](#)). Bisphosphonate therapy for the treatment of osteoporosis, at the doses indicated under prescribing information, is permitted during the study. If bisphosphonate therapy is initiated after enrollment, the reason for its use must be clearly documented clearly documented in the eCRF.

All medications (other than study drug), including anaesthetic agents, vitamins, homeopathic/herbal remedies, nutritional supplements, and significant non-drug therapies (including physical therapy and blood transfusions) starting or changing after the patient

Proprietary confidential information.

© 2016 Boehringer Ingelheim International GmbH or one or more of its affiliated companies. All rights reserved.

This document may not - in full or in part - be passed on, reproduced, published or otherwise used without prior written permission.

signed informed consent must be listed on the concomitant medication page of eCRF including trade name, start and end dates, indication for use etc. as specified in the [Flow Chart](#). Subsequent anti-cancer therapy received after discontinuation of the study treatment must also be recorded in the eCRF for patients participating in the Phase II part of the study.

If patients receive parenteral nutrition during the trial, the components need not be specified in detail. It should just be indicated as “parenteral nutrition”. If a patient requires anesthesia, it will be sufficient to indicate “anesthesia” without specifying details.

In case of major surgery (as judged by the investigator), it is recommended to stop treatment with BI 836845 and/or everolimus around one week prior to the surgery, and to restart treatment after complete wound healing. If the patient can't recover within 28 days since stopping study medication, she should be removed from the study. Exception to this in patients who derive obvious clinical benefit according to the investigator's judgement could be agreed upon discussion with BI's Clinical Monitor.

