- d EOTV: If the decision to permanently discontinue all study treatments is taken during a scheduled visit, the End Of Treatment Visit (EOTV) should be performed instead of the scheduled visit (within 7 calendar days after last drug administration)
- f FU1 and Additional FU: All patients should have a follow-up 1 (FU1) visit 42 days (+7days) after the permanent discontinuation of study drugs. Patients who have not progressed and not started further treatment at FU1 should have additional limited follow-up visits at scheduled tumor assessment until progression, start of further anti-cancer treatment, consent withdrawal, lost to follow-up or death. See [Section 6.2.3](#)
- g OP: observation period every  $90 \pm 15$  days after the last follow-up visit (visit or phone contact allowed)
- h On Visits 2 and 4 of Courses 3 through 6, and on Visits 2, 3, 4 from Course 7 onwards, the study visit for patients on arm 1 (everolimus + exemestane) can be conducted via phone for collection of adverse events and concomitant medication

1. Written informed consent must be obtained before any protocol specific screening assessment is performed. Additional informed consent must be obtained prior to fresh tumor biopsy
2. Randomization: the randomization may take place up to 3 days prior to the C1V1 if site procedures require advance randomization to accommodate the logistics of dispensing study medication to patients. Sites that use this option must include a copy of site policy or documented justification in the ISF and submit a copy to the sponsor. If randomization is performed prior to C1V1, the subsequent visits must be scheduled with reference to C1V1. Arm 1 treatment: everolimus + exemestane; Arm 2 treatment: BI 836845 + everolimus + exemestane. Patient's screening, randomization and EOTV will be collected in the IRT system
3. Physical exam: includes a thorough cardiopulmonary, abdominal and lymph node exam and an assessment of the mental and neurological status. No need to repeat the physical exam on C1V1D1 if within three calendar days of the screening physical exam and the patient is deemed stable by the investigator
4. Vital signs: includes respiratory rate, pulse, temperature and blood pressure

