### 3.3.4 Removal of patients from therapy or assessments

#### 3.3.4.1 Removal of individual patients

A patient has to be withdrawn from study therapy in case any of the following applies:

1. The patient withdraws consent from study treatment
2. Documented progressive disease
3. The patient is no longer able to receive any of the study treatments (e.g. adverse events, concomitant diagnoses, surgery, concomitant medications or administrative reasons)
4. An increase in QT/QTc to >500 ms or of >60 ms over baseline
5. Significant deviation from the protocol or eligibility criteria. The decision to continue or withdraw treatment will be made after discussion between the sponsor and the investigator
6. Further dose reductions considered necessary but not allowed according to the protocol (for exceptions, refer to [Section 4.1.4.3](#))

A patient has to be considered to have completed the trial and any further study assessment (except the observation period for collection of vital status and further therapies) in case any of the following applies:

1. Documented progressive disease (refer to [Section 5.1.2](#))
2. Start of new anti-cancer treatment
3. Withdrawal of consent

If possible, a patient who discontinues treatment for reasons other than the above criteria should continue to be followed up based on the tumor assessment schedule.

All patients who are included into the trial (i.e. having given informed consent) will have their data entered into the trial database. This includes patients who are considered screen failures i.e. do not commence study drug treatment.

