#### **4.3.3 Compliance Assessment**

Patients who do not attend a minimum of 75% of scheduled study visits, unless due to exceptional circumstances, should be discussed with BI clinical monitor and be evaluated for compliance.

The investigator and/or the sponsor can withdraw a patient from the study in the event of serious and persistent non-compliance which jeopardizes the patient's safety or render study results.

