In the event of a delay, interruption or discontinuation of treatment, tumor assessment should continue to follow the original schedule. For patients who prematurely discontinue study medication including those discontinued with only clinical disease progression but without radiographic PD, tumor assessments should continue to be performed every 8 or 12 weeks as if the patient remained on study drug until criteria for end of follow-up period are met (refer to [section 6.2.3](#) for details).

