## Phase II part

*Follow-up 1 (42 + 7 days after permanent discontinuation of study drug)*

Every patient should complete the first follow-up visit. Refer to the [Flow Chart](#) for details.

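### Protocol 4.2.1.3 removes a patient who is slow to recover from surgery from the study rather than from treatment, against 3.3.4.1, 5.1.2.1 and 6.2.3; followed literally, it causes avoidable PFS censoring

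*Protocol*

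**What the plan says.** **The rule at issue.** Protocol 4.2.1.3 advises stopping drug about a week before major surgery and restarting after wound healing. It then says: "If the patient can't recover within 28 days since stopping study medication, she should be removed from the study". An exception for patients with obvious clinical benefit can be agreed with the sponsor's clinical monitor.

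**A related, weaker clause.** Protocol 4.3.3 allows the investigator or sponsor to "withdraw a patient from the study in the event of serious and persistent non-compliance which jeopardizes the patient's safety or render study results". This is discretionary.

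**The sections that point the other way:**
- 3.3.4.1 keeps two lists. Reasons to withdraw from study *therapy* include "The patient is no longer able to receive any of the study treatments (e.g. adverse events, concomitant diagnoses, surgery, concomitant medications or administrative reasons" and "Significant deviation from the protocol or eligibility criteria. The decision to continue or withdraw treatment will be made after discussion". Reasons that end study *assessments* are only documented progression, new anti-cancer treatment and withdrawal of consent. For everyone else the default, qualified by *if possible*, is that "a patient who discontinues treatment for reasons other than the above criteria should continue to be followed up based on the tumor assessment schedule".
- 5.1.2.1, on premature discontinuation of study medication: "tumor assessments should continue to be performed every 8 or 12 weeks as if the patient remained on study drug".
- Flow Chart, Phase II part, footnote f: "Patients who have not progressed and not started further treatment at FU1 should have additional limited follow-up visits at scheduled tumor assessment until progression".
- 6.2.3.2: "Every patient should complete the first follow-up visit". Follow-up then ends only for progression, new anti-cancer therapy, loss to follow-up, withdrawal of consent or death.
- 6.2.3.3 follows all Phase II patients for survival.
- 4.1.4.3 has a parallel rule: no recovery from drug-related toxicity within 28 days ends study treatment, not study participation.

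**The concern.** Surgery is on the list that ends therapy, and failure to recover from it is on no list that ends assessments. Section 4.2.1.3 nevertheless takes the patient out of the study and does not refer the reader to 3.3.4.1, 5.1.2.1 or 6.2.3.

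The stake is the primary endpoint. Once scans stop, SAP Table 5.1.2: 1 censors PFS at the last scan. If two or more consecutive assessments are missed, a later progression or death is censored back to that scan even when it is known. A patient who cannot recover from surgery may have a different prognosis from those still followed, so the censoring may be informative. Neither PFS sensitivity analysis in SAP 7.4.2.2 examines it: one adds data after the cut-off and the other changes the source of the stratification factor. Protocol 7.6 itself calls it a concern when patients leave without an event, because the trial then takes longer.

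**Working it through.** **1. What censoring does to one patient.** Windows are from SAP Table 6.7.2: 1. Day numbers for stopping drug are assumed.
- *Case A.* Drug stopped day 50, week-8 scan on day 57, removed on day 78. The scan is 78 − 57 = 21 days old, so 5.1.2.1 requires no end-of-treatment scan. The week-16 window (days 86–141) and week-24 window (142–197) are missed. A death after day 197 is censored at day 57, more than 197 − 57 = 140 days back.
- *Case B.* Drug stopped day 60, not recovered by day 88. The day-57 scan is 31 days old, so an end-of-treatment scan is due. It is done on day 88, in the week-16 window. The week-24 window (142–197) and week-32 window (198–253) are missed. A death after day 253 is censored at day 88, more than 253 − 88 = 165 days back.

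Deaths after zero or one missed assessment still count as events. Patients who start new anti-cancer therapy before an event are censored whatever 4.2.1.3 says.

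**2. Reproducing the plan's timing.** Inputs from protocol 7.6: 150 patients, 12 months' accrual, medians 10.8 and 7.8 months, 90 events, and a fraction c permanently censored.

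λ₁ = ln 2/10.8 = 0.0642 and λ₂ = ln 2/7.8 = 0.0889 per month.

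F(T) = ½ Σ [1 − (e^(−λ(T−12)) − e^(−λT))/(12λ)], the protocol's own formula.

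Solving 150(1 − c)F(T) = 90 gives T = 24.90, 27.93 and 32.54 months for c = 20%, 25% and 30%. Table 7.6: 3 states 24.9, 27.9 and 32.5, so it reproduces.

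**3. Adding removals.** The documents give no number, so 1 to 5 is an assumption. Each removal is counted as one more permanently censored patient, which is an upper bound for the reasons given under step 1.

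| Starting row | Removals | Solve | Months to 90 events |
|---|---|---|---|
| 20% (120 left) | 0 | 120·F(T) = 90 | 24.9 |
| 20% | 1 | 119·F(T) = 90 | 25.2 |
| 20% | 5 | 115·F(T) = 90 | 26.8 |
| 25% (112.5 left) | 0 | 112.5·F(T) = 90 | 27.9 |
| 25% | 5 | 107.5·F(T) = 90 | 30.8 |

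From the 20% row the delay is 25.2 − 24.9 = 0.3 to 26.8 − 24.9 = 1.9 months, still inside the 30-month limit.

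**4. Precision.** SE(log HR) = 2/√events.
- At 90 events: 2/√90 = 0.211. From the 20% row this does not change, because the analysis waits for the 90th event.
- From the 25% row, five removals pass 30 months. With F(30) = 0.828, events at 30 months are 107.5 × 0.828 = 89.0, and SE = 2/√89.0 = 0.212.
- The 30% row misses 90 events by 30 months without any removals: 105 × 0.828 = 86.9, SE 0.215. Five removals give 100 × 0.828 = 82.8, SE 0.220.

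**The case against.** **Context suggests only treatment was meant.** The sentence sits among instructions to stop and restart drug, and an exception for clinical benefit reads most naturally as a reason to keep dosing. Section 5.1.2.1 itself speaks of patients discontinuing the trial when it requires a scan at the end-of-treatment visit. Several other sections state that follow-up continues. This stands as a reason for a low grade. It does not remove the point, because the sentence is the specific rule for this situation and says the opposite.

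**Continued scanning is not absolute.** Section 3.3.4.1 qualifies it with *if possible*. This stands. The conflict is with a strong default, not an unconditional requirement.

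**Section 4.3.3 is a weaker case.** It is permissive, is limited to serious and persistent non-compliance, and follows a rule about poor visit attendance. Missed scans in a patient who does not attend are hard to call avoidable. This stands, so the main point rests on 4.2.1.3.

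**The loss may already be allowed for, and the pool is small.** Protocol 7.6 assumes 20 to 30% permanently censored, or 30 to 45 of 150 patients, and exclusion criterion 9 bars patients already scheduled for surgery. Both stand. They limit the size of the effect; they do not make the censoring necessary.

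**Stronger readings a reader might infer.** One is that the lost events come straight off the 90 and widen the confidence interval. The analysis waits for 90 events or about 30 months, so the main effect is delay. Another is bias between arms: the documents give no removal counts by arm and show no imbalance. A third is that the word *may* in 3.1 is a further conflict. That sentence defers to the Flow Chart, where footnote f says *should*, so changing it is editorial.

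**Conclusion.** The point holds as a minor one. The removal sentence in 4.2.1.3 contradicts 3.3.4.1, 5.1.2.1, 6.2.3.2 and 6.2.3.3, and a site following it literally would create PFS censoring that the rest of the protocol is written to avoid. For an affected patient, a known death can be censored back by more than 140 to 165 days. For the trial, an assumed 1 to 5 removals mean a delay of about 0.3 to 1.9 months from the 20% row and essentially no change in SE: 0.211, or about 0.212 at 30 months from the 25% row. The case rests on internal inconsistency and possibly informative censoring, not on precision.

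This assumes the removal counts above and the planned 90-event readout. The SAP follows protocol amendment 3, which is not among the supplied documents, and uses assessments to 25 November 2016. The number of events at that cut-off is not given, so the figures describe the design as planned, not the analysis finally performed.

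**What to change.** - **4.2.1.3:** replace the removal wording with *permanently discontinued from study treatment; tumour assessments, FU1 and survival follow-up continue per 3.3.4.1, 5.1.2.1 and 6.2.3*. Keep the clinical-benefit exception.
- **4.3.3:** keep the discretion to stop a non-compliant patient's treatment, and add that follow-up continues where possible unless she withdraws consent.
- **3.1 (optional, editorial):** change *may* to *should* for scans after discontinuation, to match the Flow Chart.

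The cost is a wording change in two sections, or three with the editorial one, and a few off-treatment scans that the protocol already schedules. Treatment still stops at the same point, and withdrawal of consent still ends assessments.
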